6.4.1.6 High Sensitivity C-reactive protein (hsCRP)

[figure not shown]
Blood for this assessment will be obtained in order to identify the presence of inflammation, to determine its severity, and to monitor response to treatment.

Since the results of this test may unblind study personnel, results from the central lab will be provided for Screening and Baseline only. The hsCRP results from samples collected during the treatment period will be revealed following database lock only.

6.4.1.7 Erythrocyte sedimentation rate (ESR)

Blood for ESR, which is helpful in diagnosing inflammatory diseases and is used to monitor disease activity and response to therapy, will be obtained at scheduled visits as indicated in Table 6-1.

Confidential

Page 58

Presence of enthesitis

Novartis

If enthesitis is present with any of the 6 sites, the subject is counted as a subject with enthesitis.

6.4.8 Psoriasis Area and Severity Index (PASI)

The PASI (Fredriksson 1978; Weisman 2003; Gottlieb 2005) assesses the extent of psoriasis on four body surface areas (head, trunk and upper and lower limbs) and the degree of plaque erythema, scaling and thickness. A PASI score will be derived as indicated in Table 6-3.

The head, trunk, upper limbs and lower limbs are assessed separately for erythema, thickening (plaque elevation, induration) and scaling (desquamation). The average degree of severity of each sign in each of the four body regions is assigned a score of 0-4. The area covered by lesions on each body region is estimated as a percentage of the total area of that particular body region. Further practical details help the assessment:

- The neck is assessed as part of the head.
- The axillae and groin are assessed as part of the trunk.
- The buttocks are assessed as part of the lower limbs.

When scoring the severity of erythema, scales should not be removed.

Table 6-3 The PASI scoring system

Body region	Erythema	(E)	Thickening (plaque elevation, induration, I)	Scaling (desquamation, D)	Area score (based on true area%, A)*
Head (H) [†]	0=none		0=none	0=none	0 = no involvement
	1=slight 2=moderate		1=slight 2=moderate	1=slight 2=moderate	1 = >0-< 10%
	3=severe 4=very severe		3=severe 4=very severe	3=severe 4=very severe	2 = 10-<30%
	•		-	-	3 = 30-<50%
					4 = 50-<70%
					5 = 70-<90%
					6 = 90-100%
Trunk (T) [‡]	0=none		0=none	0=none	0 = no involvement
	1=slight 2=moderate		1=slight 2=moderate	1=slight 2=moderate	1 = >0-< 10%
	3=severe 4=very severe		3=severe 4=very severe	3=severe 4=very severe	2 = 10-<30%
					3 = 30-<50%
					4 = 50-<70%
					5 = 70-<90%
					6 = 90-100%
Upper	0=none		0=none	0=none	0 = no involvement
limbs (U)	1=slight 2=moderate		1=slight 2=moderate	1=slight 2=moderate	1 = >0-< 10%
	3=severe 4=very severe		3=severe 4=very severe	3=severe 4=very severe	2 = 10-<30%
					3 = 30-<50%
					4 = 50-<70%
					5 = 70-<90%
					6 = 90-100%

Body region	Erythema	(E)	Thickening (plaque elevation, induration, I)	Scaling (desquamation, D)	Area score (based on true area%, A)*
Lower	0=none		0=none	0=none	0 = no involvement
limbs (L) [§]	1=slight 2=moderate		1=slight 2=moderate	1=slight 2=moderate	1 = >0-< 10%
	3=severe 4=very severe		3=severe 4=very severe	3=severe 4=very severe	2 = 10-<30%
					3 = 30-<50%
					4 = 50-<70%
					5 = 70-<90%
					6 = 90-100%

^{*} Percentage (not score) of body region (not whole body) affected will be entered in the eCRF

The head and neck, upper limbs, trunk and lower limbs correspond to approximately 10%, 20%, 30% and 40% of the body surface area, respectively; the PASI score is calculated using the following formula:

$$PASI = 0.1(E_H + I_H + D_H)A_H + 0.2(E_U + I_U + D_U)A_U + 0.3(E_T + I_T + D_T)A_T + 0.4(E_L + I_L + D_L)A_L$$

where E = erythema; I = induration; D = desquamation; A = area; H = Head; U = Upper limbs; T = Trunk; and L = Lower limbs

PASI scores can range from a lower value of 0, corresponding to no signs of psoriasis, up to a theoretic maximum of 72.0. The investigator is responsible for collecting the components or scoring signs and total regional area. More information is provided in Appendix 5.

6.4.10 Appropriateness of efficacy assessments

The efficacy outcome measures used in this study are the standard measures used across many PsA trials.

[†] Neck is assessed as part of the Head (H) body region.

[‡] Axillae and groin are assessed as part of the Trunk (T) body region.

[§] Buttocks are assessed as part of the Lower limbs (L) body region.

6.5 Safety

Evaluation of all AEs and SAEs including injection site reactions, abnormal findings in ECG, physical examination, vital signs and laboratory assessments will occur.

All blood draws and safety assessments should be done prior to study treatment administration. Appropriate safety assessments (e.g. evaluation of AEs and SAEs including injection site reactions) should be repeated after the dose is administered.

- Evaluation of AE/ SAEs
- Physical examination
- Vital signs
- Height and weight
- QuantiFERON TB-Gold test or PPD skin test
- Electrocardiogram
- Local tolerability (injection site reactions)
- Laboratory evaluations (Hematology, Clinical Chemistry, Lipid Panel, Urinalysis)
- Pregnancy and assessment of fertility
- Tolerability of secukinumab and adalimumab

6.5.1 Physical examination

The physical examination will include the examination of general appearance, skin, neck, eyes, ears, nose, throat, lungs, heart, abdomen, back, lymph nodes, extremities, vascular and neurological system.

Information for all physical examinations must be included in the source documentation at the study site. Significant findings that are present before signing the ICF must be included in the relevant medical history eCRF. Significant findings made after signing the ICF which meet the definition of an AE must be recorded in the Adverse Event eCRF.

6.5.2 Vital signs

Vital signs will include blood pressure and pulse rate measurements after 5 minutes rest in sitting position. If possible, vital signs assessments should be performed by the same study site staff member using the same validated device throughout the study.

6.5.3 Height and weight

Height in centimeters (cm) and body weight, to the nearest 0.1 kilogram (kg), in indoor clothing but without shoes, will be measured.

If possible, body weight assessments should be performed by the same study site staff member using the same scale throughout the study.

6.5.4 QuantiFERON TB-Gold test or PPD skin test

Either a QuantiFERON TB-Gold test or a PPD skin test must be performed at screening. Subjects with a positive test may participate in the study if further work up (according to local practice/guidelines), establishes conclusively that the subject has no evidence of active tuberculosis, OR, if presence of latent tuberculosis is established, then treatment according to local country guidelines must have been initiated prior to enrollment.

Page 62

6.5.4.1 **QuantiFERON TB-Gold test**

A QuantiFERON TB-Gold test is to be performed at the second screening visit and the results have to be known prior to randomization to determine the subject's eligibility for the trial. The test will be used to screen the subject population for latent tuberculosis infection.

The test will be performed by the central laboratory. Details on the collection, processing and shipment of samples and reporting of results by the central laboratory are provided in the laboratory manual.

6.5.4.2 PPD skin test

A PPD skin test is to be performed at screening and read before randomization to determine the subject's eligibility for the trial, if a QuantiFERON test is not performed. The test dose is bioequivalent to 5 tuberculin units of standard PPD injected intradermally, usually into the volar surface of the forearm. The site is cleaned and the PPD extract is then injected into the most superficial layer under the skin. If given correctly, the injection should raise a small wheal of about 5 mm, which resolves within 10-15 minutes.

Because the reaction (induration), will take 48-72 hours to develop, the subjects must return to the study site within that time for evaluation of the injection site. This will determine whether the subject has had a significant reaction to the PPD test. A reaction is measured in millimeters of induration (hard swelling) at the site. A PPD skin induration ≥5 mm (or according to local practice/guidelines) is interpreted as a positive result.

6.5.5 Laboratory evaluations

A central laboratory will be used for analysis of all specimens listed below (except urinalysis). Details on the collection, shipment of samples and reporting of results by the central laboratory are provided in the laboratory manual. For the identification of clinically notable values, see Appendix 6 and Appendix 7. All subjects with laboratory tests containing clinically significant abnormal values are to be followed until the values return to normal ranges or until a valid reason, other than treatment related AE, is defined.

6.5.5.1 Hematology

Hemoglobin, platelets, red blood cell (RBC), white blood cell (WBC) and differential white blood cell counts will be measured at scheduled visits.

6.5.5.2 Clinical chemistry

Serum chemistries will include glucose, urea, creatinine, total bilirubin, AST (SGOT), ALT (SGPT), GGT, alkaline phosphatase, sodium, potassium, bicarbonate, calcium, phosphorus, total protein, albumin, and uric acid.

6.5.5.3 Urinalysis

Dipsticks will be provided by the central laboratory to the sites for local urinalysis assessments. The urinalysis results for standard parameters such as protein, glucose, blood, and WBCs will be recorded in the appropriate eCRF.

Lipid panel 6.5.5.4

A lipid profile including High Density Lipoprotein (HDL), Low Density Lipoprotein (LDL), total cholesterol, and triglycerides will be measured from a fasting blood sample.

6.5.6 Electrocardiogram (ECG)

A standard 12-lead ECG will be performed as indicated in Table 6-1 at the Baseline visit. ECGs must be recorded after 10 minutes rest in the supine position to ensure a stable baseline. The preferred sequence of cardiovascular data collection during study visits is ECG collection followed by vital signs and blood sampling. The Fridericia QT correction formula (QTcF) should be used for clinical decisions.

Each ECG tracing should be labeled with study number, subject initials, subject number, date and time, and filed in the study site source documents. For any ECGs with subject safety concerns, two additional ECGs should be performed to confirm the safety finding. Clinically significant ECG findings at baseline must be discussed with the sponsor before administration of investigational treatment.

Clinically significant abnormalities must be recorded on the relevant section of the medical history/Current medical conditions/AE eCRF as appropriate.

6.5.7 Pregnancy and assessments of fertility

The study treatment must not be given to pregnant women; therefore, effective methods of birth control must be used for women of childbearing potential (see exclusion criteria definitions, Section 4.2).

A serum β-hCG test will be performed in all women at screening. All women who are not surgically sterile or post-menopausal (as defined in Section 4.2) at screening, will have local urine pregnancy tests as indicated in Table 6-1. A positive urine pregnancy test requires immediate interruption of study treatment until serum β-hCG is performed and found to be negative. If positive, the subject must discontinue study treatment.

[figure not shown]
6.5.8 **Tolerability of Investigational Treatments**

Tolerability will be assessed by AEs, laboratory values, injection site reaction,

6.5.9 Additional parameters

Blood will be obtained at the first screening visit (Visit 1) for anti-CCP antibodies and the Rheumatoid Factor (RF) assessment. Antinuclear antibody (ANA) and anti-double stranded deoxyribonucleic acid antibody (anti-dsDNA) antibodies will also be assessed at visits/time points indicated in Table 6-1.

6.5.11 Appropriateness of safety measurements

The safety measures used in this study are standard for a use of a biologic in patients with PsA. A chest X-ray or MRI at screening (or within 3 months prior to screening) is performed to rule out the presence of a pulmonary malignancy of infectious process (in particular, tuberculosis).

[figure not shown]
The total amount of radiation exposure that results from the screening X-ray measurement is considered to involve minimal risk and is necessary to ensure reliable safety measures before the treatment with a biologic.

The safety assessments selected are standard and adequate for this indication/subject population.

6.6 Other assessments

[figure not shown]
The other assessments planned for the study are:

• Quality of Life questionnaires/ Patient reported outcomes (PROs)

6.6.1 Health-related Quality of Life

[figure not shown]
The impact of PsA on various aspects of subjects' health-related quality of life (HRQoL) will be assessed using the following validated instruments:

All questionnaires will be available, where possible, in the local languages of the participating countries and should be completed by subjects before they see the study physician. All questionnaires will be completed at the defined visits / time points listed in the Table 6-1 and prior to the subject seeing the investigator for any clinical assessment or evaluation. The questionnaires will be in the respondent's local language. The subject should be given sufficient instruction, space, time and privacy to complete the questionnaires. The study coordinator should check the questionnaires for completeness and encourage the subject to complete any missing responses. Completed questionnaires should be reviewed and assessed by the investigator, before the clinical examination, for responses which may indicate potential AEs or SAEs. This assessment should be documented in the source records. If AEs or SAEs are confirmed, the investigator should record the events as per instructions given in the relevant section of the protocol (see Section 7.1 and Section 7.2).

Guidelines for administering the PRO questionnaires can be found in Appendix 2.

[figure not shown]

Confidential

Novartis

Page 67

7 Safety monitoring

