6.4 Efficacy

The efficacy outcome measures used in this study are standard measures used across all PsA trials.

- American College of Rheumatology (ACR) 20, 50 responses
 - Swollen Joint Count (SJC)/Tender Joint Count (TJC)
 - Patient's global assessment of disease activity (VAS)
 - Physician's global assessment of disease activity (VAS)
 - Patient's assessment of PsA pain intensity (VAS)
 - Health Assessment Questionnaire Disability Index (HAQ-DI[©])
 - high sensitivity C-Reactive Protein (hsCRP) and Erythrocyte Sedimentation Rate (ESR)

All efficacy assessments should be performed prior to administration of study treatment. Details relating to the administration of all PROs are provided in Appendix 2.

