6.4.1.4 Physician's global assessment of disease activity

The physician's global assessment of disease activity will be performed using a 100 mm VAS ranging from no disease activity to maximal disease activity, after the question 'Considering all the ways the disease affects your patient, draw a line on the scale for how well his or her condition is today'. To enhance objectivity, the physician must not be aware of the specific subject's global assessment of disease activity, when performing his own assessment on that subject.

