A personal history of psoriasis is defined as a history of psoriasis that may be obtained from a patient, family physician, dermatologist, rheumatologist, or other qualified health care provider. (1 points)

A family history of psoriasis is defined as a history of psoriasis in a first- or second- degree relative according to patient report. (1 points)

Typical psoriatic nail dystrophy including onycholysis, pitting, and hyperkeratosis observed on current physical examination (1 point)

A negative test result for the presence of rheumatoid factor by any method except latex (1 point)

Either current dactylitis, defined as swelling of an entire digit, or a history of dactylitis recorded by a rheumatologist (1 point)

Radiographic evidence of juxta-articular new bone formation appearing as ill-defined ossification near joint margins (but excluding osteophyte formation) on plain radiographs of the hand or foot (1 point)

Total score:

(The CASPAR criteria eCRF will autopopulate the total number of points of the CASPAR criteria met by the subject. If the total score ≥ 3 , the subject meets CASPAR criteria for PsA diagnosis.)

* Current psoriasis is assigned a score of 2; all other features are assigned a score of 1

14 Appendix 2: Guidelines for administering the questionnaires for patient reported outcomes

Before trial start

Study coordinators should familiarize themselves with the PRO questionnaire(s) in the trial and identify any items where a patient's response might highlight issues of potential concern.

Before completion

Subjects should be provided with the correct questionnaire at the appropriate visits and in the appropriate language

Subjects should have adequate space and time to complete the forms

Patients should be provided with a firm writing surface (such as a table or a clip board)

Questionnaire should be administered before the clinical examination

During completion

Administrator may clarify the questions but should not influence the response

Only one response for each question

Also see "Addressing Problems and Concerns"

After completion

Check for completeness and not for content*

Data should be sent from the eCRF / electronic device

Data should be reviewed by Investigator for AEs

*However, any response which may directly impact or reflect the patient's medical condition (e.g. noting of depression) should be communicated by the study coordinator to the investigator).

Addressing Problems and Concerns

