Emphasize that all responses are to be kept confidential. Point out that their names do not appear anywhere on the questionnaire, so that their results will be linked with an ID number and not their name. Tell the patient that his/her answers will be pooled with other patients' answers and that they will be analyzed as a group rather than as individuals. Tell the patient that completed forms are not routinely shared with treating staff and that their responses will only be seen by you (to check for completeness) and by the investigator. Any response which may directly impact on or reflect their medical condition (*e.g.* noting of severe depression) will be communicated by the coordinator to the physician.

The patient asks the meaning of a question/item

While completing the questionnaire, some patients might ask the meaning of specific items so that they can better understand and respond. If this happens, assist the patient by rereading the question for them *verbatim*. If the patient asks to interpret the meaning of an item, do not try to explain it, but suggest that he/she use his/her own interpretation of the question. Patients should answer the questions based on what *they* think the questions mean.

A General Information about all questionnaire(s):

All questionnaires have to be completed by the patients in their local languages using an electronic device. The questionnaires should be completed by the patients in a quiet area free from disturbance, and before any visit assessments. Patients should receive no help from family members; if questions cannot be answered alone (due to problems with reading or understanding), then the doctor or nurse should read the questions and record the patient's responses without influencing their answers. The information provided is strictly confidential and will be treated as such. If a patient has missed a question or given more than one response

per question, then this should be brought to patient. Incomplete questions should not be accepted without first encouraging the patient to complete unanswered questions.

The investigator must complete the patient/visit information on the electronic device and ensure that the center number, patient's number and initials are identical to the CRF. As there are no source data for this questionnaire, the data queries will be restricted to patient/visit information.

15 Appendix 3: American College of Rheumatology (ACR) Measures and Criteria of Response

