The patient's global assessment of disease activity will be performed using 100 mm VAS ranging from "very good" to "very poor", after the question "*Considering all the ways psoriatic arthritis affects you, please indicate with a vertical mark (|) through the horizontal line how well you are doing today*".

Physician's global assessment of PsA disease activity

[figure not shown]
The physician's global assessment of disease activity will be performed using 100 mm VAS ranging from no disease activity to maximal disease activity, after the question "*Considering all the ways the disease affects your patient, draw a line on the scale for how well his or her condition is today*". To enhance objectivity, the physician must not be aware of the specific patient's global assessment of disease activity, when performing his own assessment on that patient.

[figure not shown]
Erythrocyte sedimentation rate (ESR)

Blood for ESR, which is helpful in diagnosing inflammatory diseases and is used to monitor disease activity and response to therapy, will be obtained at scheduled visits.

High-sensitivity C-reactive protein (hsCRP)

[figure not shown]
Blood for this assessment will be obtained in order to identify the presence of inflammation, to determine its severity, and to monitor response to treatment. Since the results of this test may unblind study personnel, results from the central lab will be provided for screening and baseline only. The hsCRP results from samples collected during the treatment period will be revealed following database lock only.

Presence of enthesitis

If enthesitis based on LEI is present with any of the 6 sites (lateral epicondyle humerus L + R, proximal achilles L + R and medial condyle femur L + R), the patient is counted as a patient with enthesitis.

Resolution of enthesitis

Resolution of enthesitis (based on LEI [REDACTED]) is defined as absence of enthesitis at any post-baseline visit in subjects included in the Enthesitis subset (LEI [REDACTED]).

Psoriasis Area and Severity Index (PASI)

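### The rule that the physician scores the global VAS unaware of the patient's global VAS is not protected by the questionnaire procedures

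*Protocol*

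**What the plan says.** **Masking rule.** Protocol 6.4.1.4, on the physician's global assessment, says "the physician must not be aware of the specific subject's global assessment of disease activity" when making his or her own rating. SAP 2.12.3.1 repeats it: "the physician must not be aware of the specific patient's global assessment of disease activity".

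**Review rule.** Protocol 6.6.1 says: "Completed questionnaires should be reviewed and assessed by the investigator, before the clinical examination". The stated purpose is to find responses that may point to adverse events. The same section has patients complete the questionnaires before they see the study physician or investigator.

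**Reach of the review.** Protocol 6.4 lists the patient's global VAS, the pain VAS and HAQ-DI among the efficacy measures and adds: "Details relating to the administration of all PROs are provided in Appendix 2". Appendix 2 says "Data should be reviewed by Investigator for AEs", and its script for worried patients says that "their responses will only be seen by you (to check for completeness) and by the investigator". It exempts no item.

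**Who may record answers.** For patients who cannot answer alone because of reading or comprehension problems, Appendix 2 says "then the doctor or nurse should read the questions and record" the responses. For patients too ill or weak, the same appendix allows help from the designated study coordinator only.

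**Raters.** Protocol 6.4.1.1 names independent assessors for the joint counts. No section names a separate rater for the physician's global VAS.

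**The concern.** Both global VAS items are among the five domains of which three must improve for ACR20 (the primary endpoint) and ACR50 (H3). Three of the five are patient-reported, one is a laboratory value, and the physician's global is the only physician rating. The sponsor masks that rating, in the protocol's own terms, to make it more objective.

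If the investigator who reads the questionnaires also scores the VAS, the review comes before the examination and the patient's global is known before the physician's item is marked. One patient perception could then supply two of the three domains needed. What would be lost is a safeguard that the plan itself set for a primary-endpoint component.

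**Working it through.** **1. The texts side by side**

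| Question | Answer in the plan | Where |
|---|---|---|
| May the rating physician know the patient's global VAS? | No | Protocol 6.4.1.4; SAP 2.12.3.1 |
| When does the investigator read the questionnaires? | Before the clinical examination | Protocol 6.6.1 |
| Does the investigator's review reach the patient's global VAS? | All PROs are sent to Appendix 2, which includes the review; no exemption | Protocol 6.4; Appendix 2 |
| Is the physician's VAS scored before the review? | Not stated | – |
| Is the rater someone other than the reviewing investigator? | Not stated; independent assessors for joint counts only | Protocol 6.4.1.1 |
| Who may record a patient's answers? | Doctor or nurse in one place, coordinator only in another | Appendix 2 |

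A site where one person is both reviewer and rater can therefore comply with 6.6.1 and Appendix 2 and breach 6.4.1.4.

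**2. The plan's own figure**

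Inputs (Protocol 9.7): n = 425 per arm, 62% against 50%, two-sided alpha 0.05. Pooled chi-square, no continuity correction:

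- pooled rate = (0.62 + 0.50)/2 = 0.56
- z = [0.12 × √425 − 1.960 × √(2 × 0.56 × 0.44)] / √(0.62 × 0.38 + 0.50 × 0.50)
- z = (2.474 − 1.376)/0.697 = 1.576, so power = 94.2%

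This reproduces the stated 94%. The point alters none of these inputs.

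**3. How copying changes a patient's status**

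Let A be improvement in the patient's global, B in the physician's global, and S the number of the other three domains improved. Without copying, the 3-of-5 criterion is A + B + S ≥ 3. With full copying it is 2A + S ≥ 3. Status differs in only two cases:

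- gained: A = 1, B = 0, S = 1
- lost: A = 0, B = 1, S = 2

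Share changed = P(gained) + P(lost). Fall in response rate = P(lost) − P(gained). Copying in a random half of patients halves both. For ACR20, both joint counts must also improve, so each case counts only when they do.

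**4. Size, as an illustration**

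Assumptions, none from the documents: each of the five domains and two joint counts improves by at least 20% with the same probability, 0.6 or 0.7, and every pair has the same latent normal correlation, 0.4 to 0.6. Simulation of 1,000,000 patients per setting:

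| Probability | Correlation | 3-of-5 changed, full copying | ACR20 changed, full | ACR20 changed, half | Fall in ACR20 rate, full |
|---|---|---|---|---|---|
| 0.6 | 0.4 | 10.9% | 3.6% | 1.8% | 1.1 points |
| 0.6 | 0.5 | 9.6% | 3.1% | 1.6% | 0.9 |
| 0.6 | 0.6 | 8.2% | 2.6% | 1.3% | 0.8 |
| 0.7 | 0.4 | 9.2% | 3.5% | 1.8% | 1.3 |
| 0.7 | 0.5 | 8.3% | 3.0% | 1.5% | 1.1 |
| 0.7 | 0.6 | 7.2% | 2.6% | 1.3% | 0.9 |

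The endpoint figures are the ACR20 columns. The 3-of-5 column describes one part of the criterion and is roughly three times as large. Before copying, these settings give ACR20 rates of about 36% to 53%, so they are not calibrated to the plan's 50% and 62%.

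**The case against.** **The review rule may not reach this item.** It sits in the quality-of-life section, whose instrument list is not visible in the public copy, while the patient's global VAS is specified under Efficacy. Appendix 2, to which 6.4 refers, gives no timing for the review relative to the examination. So the conflict is assembled from several sections. This stands as a limit on how firmly it can be stated. It does not remove the conflict, because Appendix 2 covers all PROs, exempts none and does not place the review after scoring.

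**A careful site can obey both rules.** It could leave the global VAS out of the adverse-event review, or use different people. That is true, but no text tells it to. The plan permits compliance without securing it.

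**Stronger readings that the documents do not support.**

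- A reader might infer that the two ACR components are in fact not independent. The documents show only that independent scoring is unprotected; they never say that the reviewing investigator scores the VAS. All ACR components are also likely to correlate, since they describe the same disease.
- A reader might extend the masking rule to pain and HAQ-DI. It covers the patient's global assessment only.
- A reader might take recording by the doctor as routine. It is a fallback for patients who cannot answer alone.
- A reader might infer bias between arms, because Protocol 5.1.1 says that adalimumab and its placebo differ in appearance from the secukinumab supplies. Section 5.4 provides for physical barriers, a separate drug administrator and advice not to comment on appearance. Section 3.1 keeps assessors blinded, and the questionnaire procedure is the same in both arms. Bias would need patients to guess their treatment, which nothing here shows.

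**Conclusion.** The point holds as an unprotected safeguard: the plan masks the physician's global VAS, and its questionnaire procedures allow that masking to be broken. At stake is independent scoring of one of five ACR domains, which feeds the primary endpoint and H3.

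The likely effect is small. Full copying is an extreme that no document suggests, so 2.5% to 3.6% of patients changing ACR20 status is an upper bound under the stated assumptions. Those are equal probabilities, equal correlations, and joint counts that behave like the other items. Half copying gives about 1.3% to 1.8%. The fall of 0.8 to 1.3 points in response rates under full copying is not a difference between arms. Sample size, alpha and the 94% power are untouched. The correction is worth making because it restores the sponsor's own rule at almost no cost.

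**What to change.** 1. **Section 6.6.1.** State that the investigator's adverse-event review of the questionnaires takes place after the physician's global VAS has been recorded and before study drug is given. Alternatively, withhold the patient's global VAS from the review until the physician's VAS is recorded.
2. **Appendix 2, investigator review.** Add the same order to the sentence "Data should be reviewed by Investigator for AEs". Leave unchanged the separate instruction that patients complete questionnaires before the examination. Moving that would contradict 6.6.1 and Appendix 2's own general guidance, and would expose patients' answers to the examination.
3. **Appendix 2, help with completion.** Reconcile the doctor-or-nurse text with the coordinator-only text, so that the physician who scores the global VAS does not record the patient's answers.

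Cost: a few sentences and brief site training. The adverse-event review moves slightly later within the same visit but still precedes dosing. No staff, visits or data items are added.
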